5.4. Screen Failures

Screen failures are defined as participants who consent to participate in the clinical study but are not subsequently assigned to the investigational product in the study. A minimal set of screen failure information is required to ensure transparent reporting of screen failure

participants to meet the Consolidated Standards of Reporting Trials (CONSORT) publishing requirements and to respond to queries from regulatory authorities. Minimal information includes demography, screen failure details, eligibility criteria, and any serious adverse event (SAE).

Individuals who do not meet the criteria for participation in this study (screen failure) may be rescreened.

6. STUDY INTERVENTION

Study intervention is defined as any investigational intervention(s), marketed product(s), placebo, or medical device(s) intended to be administered to a study participant according to the study protocol.

For the purposes of this protocol, the term investigational product may be used synonymously with study intervention.

6.1. Study Intervention Administered

Intervention Name	PF-06462700
Type	Biologic
Dose Formulation	Concentrate for solution for infusion
Unit Dose Strength	5 mL ampoules containing 50 mg PF-06462700 per mL
Dosage Level	40 mg/kg/day for 4 days
Route of Administration	Intravenously
Investigational Medicinal Product (IMP) and Noninvestigational Medicinal Product (NIMP)	IMP
Sourcing	Provided centrally by the sponsor
Packaging and Labeling	Study intervention will be provided in open label carton which includes 5 ampoules. Each carton will be labeled as required per country requirement.

6.1.1. Administration

Participants will undergo PF-06462700 skin test. Those with a positive skin test will not be administered PF-06462700.

PF-06462700 will be administered at a dose of 40 mg/kg/day for 4 days. PF-06462700 will be infused intravenously over no less than 4 hours. Infusion times may be extended up to 24 hours (including dilution/preparation time) to improve tolerance if necessary.

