
• To investigate the efficacy of PF-06462700 administered intravenously at 40 mg/kg/day for 4 days in Japanese participants with moderate and above aplastic anemia	
• Hematologic response at Week 24• Hematological test values at Day 4 and at Weeks 1, 2, 4, 6, 8, 10, 12 and 24 (Absolute neutrophil count, Platelet count, Reticulocyte count). In case of early termination (ET), at ET and follow-up ET.• Survival status• Transfusion independence at Weeks 12 and 24	
Population: Japanese participants with moderate and above aplastic anemia who are at least 2 years of age
 
Variable: Each secondary endpoint
 
Intercurrent events: The efficacy will be evaluated individually for each patient. Therefore, any missing data will not be imputed. All observations after prohibited concomitant medication will be included.
 
Population-level summary: Due to the limited sample size, summary statistics will not be shown.

Safety objective:	Safety endpoints:	Estimands:

• To investigate the safety of PF-	
• Treatment-emergent adverse events	N/A

06462700 administered intravenously at 40 mg/kg/day for 4 days in Japanese participants with moderate and above aplastic anemia	(TEAEs) 
• Serious AEs (SAEs) and AEs leading to discontinuation• Vital signs• Clinical laboratory values	
---	--	--

Overall Design

Study B5411003 will assess the efficacy and safety of PF-06462700 in participants with moderate and above aplastic anemia. This is a multicenter, open-label, single-arm study. The study will have a maximum duration of approximately 28 weeks. This includes an up to 4-week screening period, a 4-day treatment period and a 24-week follow-up period. This study will enroll the minimum of 3 participants. The study will be initially conducted at 3 sites.

Number of Participants

A minimum of 3 participants will be assigned to the investigational product in the study.

Intervention and Duration

The study will have a maximum duration of approximately 28 weeks. This includes an up to 4-week screening period, a 4-day treatment period and a 24-week follow-up period.

Participants will undergo PF-06462700 skin test. Those with a positive skin test will not be administered PF-06462700.

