6.1.2. Skin test

To identify those at greatest risk of systemic anaphylaxis, skin test for potential recipients is strongly recommended before commencing treatment. A conservative, conventional approach would first employ epicutaneous (prick) testing with undiluted eATG. If the subject

does not show a wheal 10 minutes after pricking, proceed to intradermal testing with 0.02 mL of a 1:1000 volume/volume (v/v) saline dilution of eATG with a separate saline control injection of similar volume. Read the result at 10 minutes: a wheal at the eATG site 3 or more mm larger in diameter than that at the saline control site (or a positive prick test) suggests clinical sensitivity and an increased possibility of a systemic allergic reaction should the drug be dosed intravenously.

The predictive value of this test has not been proven clinically. Allergic reactions such as anaphylaxis have occurred in patients whose skin test is negative. Also, skin test done as described above will not predict for later development of serum sickness. In the presence of a locally positive skin test to eATG, serious consideration to alternative forms of therapy should be given. The risk to benefit ratio must be carefully weighed. If therapy with eATG is deemed appropriate following a locally positive skin test, treatment should be administered in a setting where intensive life support facilities are immediately available and a physician familiar with the treatment of potentially life threatening allergic reactions is in attendance.

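### Sections 1.1 and 6.1.1 bar PF-06462700 after a positive skin test, but Section 6.1.2 gives conditions for infusing after that same result

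*Protocol*

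**What the plan says.** The synopsis (Protocol 1.1, Intervention and Duration) reads: "Participants will undergo PF-06462700 skin test. Those with a positive skin test will not be administered PF-06462700". Section 6.1.1 repeats both sentences, the second being: "Those with a positive skin test will not be administered PF-06462700". Neither place has a qualifier.

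Section 6.1.2 comes next and describes the procedure: a prick test first and, if no wheal appears, an intradermal test against a saline control. For the intradermal test the threshold is "a wheal at the eATG site 3 or more mm larger in diameter" than at the control site. Such a wheal, or a positive prick test, "suggests clinical sensitivity and an increased possibility of a systemic allergic reaction should the drug be dosed intravenously".

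The section closes with three sentences on what to do next. The first says: "In the presence of a locally positive skin test to eATG, serious consideration to alternative forms of therapy should be given". The second asks for risk and benefit to be weighed. The third begins "If therapy with eATG is deemed appropriate following a locally positive skin test, treatment should be administered in a setting" and goes on to require immediate life support and a physician familiar with severe allergic reactions.

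Section 6.1.2 also says that a "skin test for potential recipients is strongly recommended before commencing treatment", whereas 1.1 and 6.1.1 say that participants will undergo it.

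**The concern.** The protocol gives two answers to one bedside question: the skin test is positive, so may the drug be infused? Sections 1.1 and 6.1.1 say no. Section 6.1.2 treats it as a matter of judgement and sets out how to do it.

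The safeguard concerns anaphylaxis. By its own account, 6.1.2 uses the test to find the people at greatest risk of it. Section 2.3 lists anaphylaxis among the reported immune-mediated reactions, and Section 2.2.3.2.1 reports one patient with it in the earlier Japanese study, whose safety set was 50. That study used a different dose regimen, and the summary does not mention skin-test results, so it shows only that the event occurs.

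A site that opens the section titled Skin test and follows it could infuse such a participant believing that it complies, and would have broken 6.1.1. The life-support conditions in 6.1.2 would limit the harm but would not remove the breach.

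**Working it through.** There is no figure to reproduce. The check compares the texts.

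1. **Is the bar qualified anywhere?** It appears in two places, 1.1 and 6.1.1. Neither distinguishes local from systemic reactions or refers to an exception in 6.1.2.

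2. **Are the barred group and the conditionally treatable group the same people?** The only positive readings that 6.1.2 defines are a positive prick test and an intradermal wheal at least 3 mm larger than control. Both are local reactions at the test site. A locally positive test is therefore not a milder category outside the bar. It is what the protocol means by a positive test, so the two rules cover the same participants.

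3. **Does any text set an order of precedence?** No. Section 6.1.2 is in the body of the protocol and is not marked as background or as subject to 6.1.1. The protocol does state precedence elsewhere: Section 6.2, item 5, says that the product label overrides the reference safety document on storage.

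4. **Which action satisfies every section?** Withholding the drug does, because 6.1.2 never compels dosing. Infusing under 6.1.2 contradicts 1.1 and 6.1.1. The statement in Section 8 that waivers are not allowed points the same way. The bar is therefore the probable intention.

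5. **Is the test itself mandatory?** It is in 1.1 and 6.1.1. In 6.1.2 it is a strong recommendation. This is a smaller mismatch in the same subsection.

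6. **Does it reach the analysis?** If the bar is followed, a positive participant receives no dose. That person falls outside the full analysis set and the safety set, both of which need at least one dose (Section 9.3). Section 9.2 provides for screening enough people to reach 3 assigned and accepts more than 3. The definition of hematologic response, the estimands and the SAP listings do not depend on the skin test.

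**The case against.** The strongest reply is that the sections can be read together. The bar is a direct rule for trial participants. Section 6.1.2 is written as general product guidance about potential recipients and patients, and its last sentence is conditional, so 6.1.1 settles that condition for this trial. Harm would need a positive test, a site that overlooks a rule stated twice, and a decision to infuse. Even then, 6.1.2 requires life support and an experienced physician at hand. It also says: "The predictive value of this test has not been proven clinically".

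Much of this stands. One action is clearly compliant, the risk is possibly raised and not established, and the chain to harm is long. It does not remove the point, because nothing tells a site that 6.1.2 is background, and detailed instructions for doing what 6.1.1 forbids do not belong in the dosing section.

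A reader might infer more: that exclusion 8 leaves an eligibility gap through which locally positive participants would be dosed. The documents do not support that. The bar applies at administration, whatever a person's eligibility status. Exclusion 8 refers to hypersensitivity and gives shock only as an example, and since 6.1.2 links a positive reading to clinical sensitivity, an investigator could fairly apply the criterion to it.

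A reader might also express one affected participant as a third of the minimum sample of 3. That only divides a hypothetical person by the target number and says nothing about how likely the case is.

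**Conclusion.** The contradiction is real and should be corrected. Two sections forbid dosing after a positive skin test, and a third sets conditions for it in the same people, on a safeguard against anaphylaxis. The conclusion rests on the wording alone and on reading eATG in 6.1.2 as the study drug. Section 2.3 defines the term that way for its own text, and no other reading makes sense in 6.1.2.

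The scope is narrow. Only participants with a positive prick or intradermal test are concerned, and there may be none. The matter is one of participant safety and protocol compliance. It has no bearing on efficacy results, estimands or sample size, and it does not show that the protocol authorises dosing after a positive test.

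**What to change.** Keep the bar in 1.1 and 6.1.1 and change 6.1.2 only:

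- Delete its last three sentences, which deal with a locally positive test.
- Put in their place: *Participants with a positive prick or intradermal test as defined above will not be dosed (see Section 6.1.1).*
- Make the skin test required instead of strongly recommended.

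The cost is a wording amendment with its ethics review. Sample size, analysis sets, visits and the SAP stay as they are. The downside is that sites lose the discretion 6.1.2 appears to give for people who might have tolerated the drug, on a test of unproven predictive value. Sections 1.1 and 6.1.1 already accept that cost.

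Naming a positive test in exclusion 8 is optional and is more than a wording change. As an eligibility criterion it would have to be settled before registration. But the skin test uses study drug, and the Schedule of Activities lists it under study treatment on Day 1, the same day as registration. Section 6.2 (item 2) restricts study intervention to enrolled participants, and Section 6.3.1 withholds product until the sponsor confirms enrollment. Exclusion 8 already carries this tension, so it should be extended only if the order of skin test and registration is reconciled with those two sections.

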6.1.2. Skin test

To identify those at greatest risk of systemic anaphylaxis, skin test for potential recipients is strongly recommended before commencing treatment. A conservative, conventional approach would first employ epicutaneous (prick) testing with undiluted eATG. If the subject

does not show a wheal 10 minutes after pricking, proceed to intradermal testing with 0.02 mL of a 1:1000 volume/volume (v/v) saline dilution of eATG with a separate saline control injection of similar volume. Read the result at 10 minutes: a wheal at the eATG site 3 or more mm larger in diameter than that at the saline control site (or a positive prick test) suggests clinical sensitivity and an increased possibility of a systemic allergic reaction should the drug be dosed intravenously.

The predictive value of this test has not been proven clinically. Allergic reactions such as anaphylaxis have occurred in patients whose skin test is negative. Also, skin test done as described above will not predict for later development of serum sickness. In the presence of a locally positive skin test to eATG, serious consideration to alternative forms of therapy should be given. The risk to benefit ratio must be carefully weighed. If therapy with eATG is deemed appropriate following a locally positive skin test, treatment should be administered in a setting where intensive life support facilities are immediately available and a physician familiar with the treatment of potentially life threatening allergic reactions is in attendance.

6.2. Preparation/Handling/Storage/Accountability

1. The investigator or designee must confirm appropriate temperature conditions have been maintained during transit for all study interventions received and any discrepancies are reported and resolved before use of the study intervention, as applicable for temperature-monitored shipments.
2. Only participants enrolled in the study may receive study intervention and only authorized site staff may supply or administer study intervention. All study interventions must be stored in a secure, environmentally controlled, and monitored (manual or automated recording) area in accordance with the labeled storage conditions with access limited to the investigator and authorized site staff. At a minimum, daily minimum and maximum temperatures for all site storage locations must be documented and available upon request. Data for nonworking days must indicate the minimum and maximum temperature since previously documented for all site storage locations upon return to business.
3. The investigator, institution, or the head of the medical institution (where applicable) is responsible for study intervention accountability, reconciliation, and record maintenance (i.e., receipt, reconciliation, and final disposition records). All study interventions will be accounted for using an investigational product accountability form/record.
4. Further guidance and information for the final disposition of unused study interventions are provided in the investigational product manual (IP manual).
5. Any storage conditions stated in the SRSD will be superseded by the storage conditions stated on the product label.
6. Study interventions should be stored in their original containers and in accordance with the labels.

7. See the IP manual for storage conditions of the study intervention once diluted.
8. Any excursions from the study intervention label storage conditions should be reported to Pfizer upon discovery along with any actions taken. The site should actively pursue options for returning the study intervention to the storage conditions described in the labeling, as soon as possible. Once an excursion is identified, the study intervention must be quarantined and not used until Pfizer provides permission to use the study intervention. It will not be considered a protocol deviation if Pfizer approves the use of the study intervention after the temperature excursion. Use of the study intervention prior to Pfizer approval will be considered a protocol deviation. Specific details regarding the definition of an excursion and information the site should report for each excursion will be provided to the site in the IP manual.
9. The sponsor or designee will provide guidance on the destruction of unused study intervention (e.g., at the site). If destruction is authorized to take place at the investigator site, the investigator must ensure that the materials are destroyed in compliance with applicable environmental regulations, institutional policy, and any special instructions provided by Pfizer, and all destruction must be adequately documented.

Additional details about accountability, storage, destruction, and excursion reporting can be found in the IP manual.

6.2.1. Preparation and Dispensing

Detailed instructions for PF-06462700 on how to prepare the investigational product for administration are provided in the current IP Manual. The investigational product will be dispensed at each visit from Day 1 to Day 4. A qualified staff member (e.g. physician, nurse, pharmacist, medical staff) will dispense the investigational product, in quantities appropriate for the study visit schedule.

6.3. Measures to Minimize Bias: Randomization and Blinding

6.3.1. Allocation to Investigational Product

Registration will be performed centrally by the sponsor or designee for all participants. Following full assessment and determination that the participant meets all eligibility criteria, the investigator or designee will fax or email a complete the registration form to the sponsor or designee. The sponsor or designee will assign a participant identification number, which will be used on all case report form (CRF) pages and other trial-related documentation or correspondence referencing that participant and fax or email to the site.

No participant shall receive investigational product until the investigator or designee has received the above information from the sponsor or designee: confirmation of the participant's enrollment.

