5.2. Exclusion Criteria

Participants are excluded from the study if any of the following criteria apply:

Medical Conditions:

1. Eligible and willing to have a sibling allogeneic stem cell transplantation.

2. Evidence of a myelodysplastic syndrome (except for refractory cytopenia in children), as well as other primitive marrow disease.
3. History or clinical suspicion of congenital aplastic anemia (Fanconi anemia, Congenital keratosis, etc).
4. History of malignant tumors with active disease within 5 years from study participation.
5. Participants who are clearly infected with hepatitis B virus (HBV), hepatitis C virus (HCV), human immunodeficiency virus (HIV), and human T-cell leukemia virus type 1 (HTLV-1).
6. Pregnant or breast-feeding participants.
7. Participants with severe hepatic, renal or cardiac failure, or any other life-threatening concurrent [aspartate aminotransferase (AST) or alanine aminotransferase (ALT) or total bilirubin values $>5 \times$ upper limit of normal (ULN), and/or creatinine value $>2 \times$ ULN].
8. Participants with hypersensitivity such as shock after skin test of this study drug.
9. Participants with uncontrolled severe infection (pneumonia, sepsis, etc).
10. Participants who received live vaccine or live attenuated vaccine within 6 weeks prior to the first dose of study drug.
11. Other acute or chronic medical or psychiatric condition including recent (within the past year) or active suicidal ideation or behavior or laboratory abnormality that may increase the risk associated with study participation or investigational product administration or may interfere with the interpretation of study results and, in the judgment of the investigator, would make the participant inappropriate for entry into this study.

Prior/Concomitant Therapy:

12. Prior immunosuppressive therapy with lymphocyte-depleting agents/therapies, including both non-B-cell selective and B-cell-depleting agents (e.g., alefacept, alemtuzumab, rituximab). However, participants previously treated with rATG may enroll.
13. Previous history of stem cell transplantation.

Prior/Concurrent Clinical Study Experience:

14. Previous administration with an investigational drug within 30 days (or as determined by the local requirement) or 5 half-lives preceding the first dose of investigational product used in this study (whichever is longer).

Diagnostic Assessments:

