8.3.1. Time Period and Frequency for Collecting AE and SAE Information

The time period for actively eliciting and collecting AEs and SAEs (“active collection period”) for each participant begins from the time the participant provides informed consent, which is obtained before the participant’s participation in the study (ie, before undergoing any study-related procedure and/or receiving investigational product), through the last study visit (Week 24 visit or Follow-up visit of ET case).

For participants who are screen failures, the active collection period ends when screen failure status is determined.

Medical occurrences that begin before the start of study intervention but after obtaining informed consent will be recorded on the Medical History/Current Medical Conditions section of the case report form (CRF), not the AE section.

Follow-up by the investigator continues throughout and after the active collection period and until the event or its sequelae resolve or stabilize at a level acceptable to the investigator, and Pfizer concurs with that assessment.

Investigators are not obligated to actively seek AEs or SAEs after conclusion of the study participation. However, if the investigator learns of any SAE, including a death, at any time after a participant has been discharged from the study, and he/she considers the event to be reasonably related to the study intervention or study participation, the investigator must promptly notify the sponsor.

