9.3. Analysis Sets

For purposes of analysis, the following analysis sets are defined:

Analysis Set	Description
Enrolled	“Enrolled” means a participant’s, or their legally authorized representative’s, agreement to participate in a clinical study following completion of the informed consent process. Potential participants who are screened for the purpose of determining eligibility for the study, but do not participate in the study, are not considered enrolled.
Full analysis set (FAS)	All participants assigned to investigational product and who take at least 1 dose of investigational product. For participants who discontinue study and/or receive blood transfusion or prohibited concomitant medication, any missing data will not be imputed and all observations after blood transfusion or prohibited concomitant medication will be included in the analysis.
Safety	All participants assigned to investigational product and who take at least 1 dose of investigational product.

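### The status and order of the Day 1 skin test are undefined, and on the only workable reading a skin-test reaction can be absent from the safety listings

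*Protocol*

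**What the plan says.** **Registration.** Protocol Section 6.3.1 places registration at this point: "Following full assessment and determination that the participant meets all eligibility criteria". It then says "No participant shall receive investigational product until the investigator or designee has received the above information", that information being the sponsor's confirmation of enrollment. Section 6.2 repeats the bar: "Only participants enrolled in the study may receive study intervention".

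**Skin test.** Exclusion 8 in Section 5.2 covers "Participants with hypersensitivity such as shock after skin test of this study drug". Section 6.1.2 describes a test made with the product, first undiluted by prick and then diluted 1:1000 intradermally: the approach "would first employ epicutaneous (prick) testing with undiluted eATG". The same section introduces the test with the words "skin test for potential recipients is strongly recommended before commencing treatment". The Schedule of Activities marks registration and the skin test on Day 1. The skin-test row stands after the registration row, under the study-treatment heading.

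**After a reaction.** Section 6.1.1 says that people with a positive test are not given the product. Section 6.1.2 allows for therapy after a locally positive test.

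**Recording.** AE collection starts at consent (Section 8.3.1). The same section sends events that begin after consent but before the start of study intervention to the Medical History page instead of the AE section. It adds: "For participants who are screen failures, the active collection period ends when screen failure status is determined". Section 5.4 keeps a minimal record for screen failures, and any SAE is part of it.

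**Analysis.** The Safety set in protocol Section 9.3 and SAP Section 4 is "All participants assigned to investigational product and who take at least 1 dose of investigational product". SAP Section 6.5 runs all safety analyses on that set. SAP Section 3.5.1 calls an event treatment-emergent if it starts on or after Day 1, and glosses Day 1 as the start of administration.

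**The concern.** A site has to know exclusion 8 before it can register a participant. It learns exclusion 8 only by applying the product to the skin. Yet it may give no product before registration is confirmed. Whether these rules conflict depends on what the skin test is, and neither document says. Sections 5 and 8 of the protocol allow no waivers, so sites need an order that they can follow as written.

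The second issue is where a reaction to the test ends up. Safety is a stated objective, and immune-mediated reactions come first among the risks in protocol Section 2.3. A person who reacts to the test and is never infused has shown exactly that risk. In a trial aiming at 3 assigned participants, one such reaction missing from the listings changes what a reader sees.

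**Working it through.** The target of 3 is a feasibility number with no test or inference behind it (protocol Sections 9.1 and 9.2), so there is no planned figure to reproduce. The check is a cross-reading.

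**Step 1: can the rules be met together?** Two things are undefined: whether the test counts as receipt of product, and whether it precedes registration. That gives 2 × 2 = 4 cases.

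| Test is receipt of product? | Test relative to registration | Section 6.3.1 and exclusion 8 both met? | Reactor never infused: in Safety set? |
|---|---|---|---|
| Yes | Before | No: product given before confirmation | No: not assigned |
| Yes | After | No: registered with exclusion 8 unknown | Only if the test is also a dose |
| No | Before | Yes | No: screen failure |
| No | After | No: registered with exclusion 8 unknown | No: assigned but undosed |

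The rules fit together in 1 of 4 cases. The uninfused reactor is outside the Safety set in 3 of 4, including the one that works.

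**Step 2: which reading does the text favor?** Section 6.1.2 speaks of potential recipients tested ahead of treatment, and Section 6.1.1 separates the test from administration. Both favor the workable case. The study-treatment heading over the skin-test row in the Schedule of Activities points the other way. No statement settles it.

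**Step 3: follow a reaction through the workable case** (test is not receipt and precedes registration).

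- *Recording.* The reaction begins after consent and before study intervention, so protocol Section 8.3.1 sends it to Medical History. By date it is a Day 1 event, so the first half of the SAP Section 3.5.1 definition could make it treatment-emergent. The gloss in the same sentence could exclude it. One event has two possible destinations.
- *Reactor not infused.* This person is a screen failure under Section 5.4, has no assignment and no dose, and is outside the Safety set. The AE and SAE listings in SAP Section 6.5.1 fall under the Safety-set restriction of Section 6.5, so the reaction is not in them.
- *Serious reaction.* It is still collected and reported: collection runs from consent, Section 8.3.1.1 requires SAE reports within 24 hours, and Section 5.4 keeps SAEs for screen failures.
- *Back-up listing.* The SAP plans no listing of skin-test results or reactions.

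**Step 4: size, as an illustration.** The documents give no rate of skin-test reactions. Assume 3 infused participants and k reactors who are never infused. The share of reactors among those tested is k/(3 + k):

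- k = 0: 0/3 = 0%
- k = 1: 1/4 = 25%
- k = 2: 2/5 = 40%

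The Safety set contains 0 of these k reactors among its 3 members throughout.

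**The case against.** The strongest reply is that a workable order exists. Skin test, registration and infusion can all happen on Day 1, in that order, and the wording of Sections 6.1.1 and 6.1.2 leans that way. The Schedule of Activities assigns days and does not fix an order within a day. This stands. A reader might infer that the sequence is impossible to follow. The documents do not support that, because the loop closes only if the test counts as receipt of product.

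A second reply is that the two problems need opposite assumptions. If the test is receipt of product, the Medical History rule does not apply, since Section 6 lets investigational product and study intervention be used synonymously. If it is not receipt, there is no loop. This is also right, and it is why step 3 follows only the workable reading. The data gap does not depend on the loop.

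Third, a shock reaction would be an SAE and would reach the sponsor. This stands too. A reader might infer that a severe reaction could vanish from the safety data altogether, but Sections 5.4, 8.3.1 and 8.3.1.1 rule that out. What remains is narrower: a nonserious reaction need not reach the AE section, and even a reported SAE in an uninfused person is outside the set used for the listings.

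Fourth, the safety objective concerns the 4-day infusion regimen, so a Safety set of dosed participants is reasonable. Agreed, and the set need not change. A reader might also infer that the safety result is biased in the product's favor. With individual listings, no inference and no reaction rate, the documents support only a possible omission.

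**Conclusion.** The concern holds as an unresolved ambiguity with a definite consequence for the data. The documents leave open whether the skin test is receipt of product or a dose, and where it sits relative to registration. Section 6.3.1, exclusion 8 and the Schedule of Activities are compatible in one case of four. In that case a pre-infusion reaction goes to Medical History under the protocol, although the SAP could call it treatment-emergent. An uninfused reactor's reaction is absent from the safety listings, while a serious one is still reported as an SAE.

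The conclusion rests on two assumptions: that a skin test alone is not a dose for the Safety set, and that at least one tested person reacts and is not infused. The 1/4 against 0/3 comparison shows scale only and estimates nothing. The point deserves correction because applying the written rules produces the omission without any error by a site.

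**What to change.** 1. **Reconcile protocol Sections 5.2, 6.1.1, 6.1.2, 6.2, 6.3.1 and the Schedule of Activities.** State whether the skin test counts as receipt of investigational product, whether it counts as a dose, and where it stands relative to registration. Sections 6.1.1 and 6.1.2 also need to agree on what follows a positive test. The clinical rule is for the sponsor and is not proposed here.
2. **Recording.** State in protocol Section 8.3.1 and SAP Section 3.5.1 that events from the time of the skin test are recorded as AEs. This removes the clash between Medical History and treatment-emergent status.
3. **Listing.** Add to SAP Section 6.5.1 one listing of skin-test results and reactions for everyone tested, flagging those who had the skin test only. Leave the Safety set otherwise unchanged.

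The cost is minor wording in both documents and one extra listing. No visit, test or participant is added.
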